4.3 Study Enrollment Procedures

Participants will be approached by the following methods:

For subjects ages 13-21 years old: either while they are an inpatient post-transplant or at any follow-up outpatient clinic visit by a study member to participate in this study.

For subjects >21 years old: either while they are an inpatient post-transplant or at their first post-op outpatient clinic visit by a study team member to participate in this study.

For all subjects:

When feasible to conduct in-person consenting, written consent will be obtained explaining the purpose of the study, their part in it, and that they can withdraw from the study at any time. As much time as necessary will be allowed for obtaining consent. Assent will be obtained from participants age 13-17 years, along with parental consent.

Additionally, we will make provisions for phone consent and enrollment if needed due to potential COVID-19 restrictions so that enrollment may proceed according to plan. If unable to conduct in-person consenting and enrollment process, patients will be contacted by phone and the study team will conduct the appropriate oral consent/assent procedures and conduct the procedures listed below remotely.

We will use block randomization to assign participants to the intervention or the control group using random block sizes ranging from 2 to 8. Block randomization will improve the probability of balanced groups over the course of the study as well as during shorter time horizons. A research data analyst, blind to the group allocations, will generate a list of sequential group assignments using this method. The list will be used to create sequentially numbered, sealed envelopes that will be used to allocate consenting participants to the control or intervention arms of our study. Each patient will have a 50% chance to be in the intervention arm of the study.

Participant enrollment will continue until we have reached 25 participants in each arm by age (13-21 years and 22 years and older) for a total of 100 participants and we will follow study participants for 12 months. No study visits are required of research participants after enrollment, but they will complete surveys and an interview over the phone.

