We will use block randomization to assign participants to the intervention or the control group using random block sizes ranging from 2 to 8. Block randomization will improve the probability of balanced groups over the course of the study as well as during shorter time horizons. A research data analyst, blind to the group allocations, will generate a list of sequential group assignments using this method. The list will be used to create sequentially numbered, sealed envelopes that will be used to allocate consenting participants to the control or intervention arms of our study. Each patient will have a 50% chance to be in the intervention arm of the study.

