5.2.2 Blinding

Research team members responsible for enrollment and reviewing emocha app submissions will not be masked to who is in the intervention or control arm. Patients will be aware of which arm they are randomized to as well. In this sense, the study will not be blinded to patients. Furthermore, patients/families will be strongly discouraged from discussing with their clinical team to which treatment arm they are enrolled. Data extraction (labs, drug levels) will be performed by study personnel that are blinded to the treatment arm. Individuals performing data analysis will receive de-identified data that does not explicitly describe which group is intervention and which is control, but simply the code without a key. Only the PI at each site and necessary personnel performing data extraction will have the key for the code to minimize bias in data analysis.

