10.2.3 Screening and Enrollment Tracking

Recruitment and retention at the sites will be supported by a centrally managed electronic data collection (EDC) system in REDCap where data will be entered on every screening and enrollment, including inclusion and exclusion criteria met, and demographics needed for reporting. Enrollment reports will be generated monthly and reported annually as part of the renewal process.

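### Allocation from sealed envelopes by unmasked recruiters may be partly predictable; the plan does not say who holds the envelopes, and central REDCap release by age group would close the gap cheaply

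*Combined protocol and SAP*

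**What the plan says.** The synopsis and sections 4.3 and 5.2.1 describe the same procedure. Assignments come in permuted blocks, with "random block sizes ranging from 2 to 8", in a 1:1 ratio ("Each patient will have a 50% chance to be in the intervention arm of the study"). On who makes the list: "A research data analyst, blind to the group allocations, will generate a list of sequential group assignments using this method". On how it is used: "The list will be used to create sequentially numbered, sealed envelopes that will be used to allocate consenting participants". Section 5.2.1 places randomization after consent and the baseline survey.

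On masking, section 5.2.2 says: "Research team members responsible for enrollment and reviewing emocha app submissions will not be masked to who is in the intervention or control arm". Extraction of drug levels and the analysis are masked.

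On approach, section 4.3 lets patients aged 13-21 be recruited "either while they are an inpatient post-transplant or at any follow-up outpatient clinic visit by a study member". Those over 21 are approached only during the inpatient stay or at the first post-operative clinic visit. The target is 25 per arm in each age group, 100 in all, across three hospitals.

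Section 10.2.3 describes a "centrally managed electronic data collection (EDC) system in REDCap where data will be entered on every screening and enrollment". Nothing links that system to allocation. The plan does not state whether the envelopes form one central run or separate runs by site or age group, who holds and opens them, or whether they are opaque.

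**The concern.** Blocking makes the arm that is behind more likely to come next. Anyone who knows the past assignments in a run can use this by keeping a tally. Varying the block size makes certainty rare, but the average advantage remains. Staff who enrol know at least the assignments they have made themselves. The decision to approach a patient comes before consent and is not protected by randomizing after the baseline survey.

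The primary outcome is adherence, measured by MLVI with a cut at a standard deviation above 2. That is close to what a recruiter judges when thinking of a patient as reliable or struggling, and some candidates were transplanted before the study (section 4.1), so their history may be known. If the choice of whom to approach followed the guess, the arms would differ in adherence before the app was used. Masked extraction cannot correct that, and section 9 describes no covariate adjustment.

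**Working it through.** The plan gives no predictability figure, so there is none to reproduce.

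**Inputs from the documents.** Block sizes 2 to 8; ratio 1:1; three sites; 100 participants, half aged 13-21; enrolling staff unmasked.

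**Assumptions.** Block sizes 2, 4, 6 and 8, equally likely (1:1 blocks must be even; the weights are not stated). Sites of equal size: about 100/3 = 33 per site run, or about 17 if runs are also split by age. Recruiters know every allocation in the run they are guessing.

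**Step 1: guess rate in a visible run.** The rule is to guess the arm that is behind and toss a coin when tied. Expected correct guesses in a block of size 2b are b + 2^(2b-1)/C(2b,b) - 1/2:

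| Block size | Correct guesses | Rate |
|---|---|---|
| 2 | 1.500 | 75.0% |
| 4 | 2.833 | 70.8% |
| 6 | 4.100 | 68.3% |
| 8 | 5.329 | 66.6% |

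Long-run rate: (1.500 + 2.833 + 4.100 + 5.329)/(2 + 4 + 6 + 8) = 13.762/20 = 68.8%. An exact recursion for finite runs gives 68.0% for a run of 33 and 67.3% for 17. Other mixes of sizes give 67.1% to 69.3% at a run of 33.

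By simulation, a Bayes-optimal guesser who knows the size range does no better than the tally. In a run of 33, one arm is behind at about 61% of draws, and the guess is then right about 80% of the time. As a check, 0.39 × 0.50 + 0.61 × 0.80 = 0.68. The next arm is certain at only about 2% of draws.

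**Step 2: guess rate with a central list.** Simulation of one list of 100 drawn across three sites, each seeing only its own history: about 52%. Two central lists of 50, one per age group, with the same own-site view: about 53%.

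**Step 3: what steering could do with no app effect.** Assume P(MLVI >2) is 20% in likely adherers and 60% in others, with equal numbers of each, so the average risk is 40%. Let c be the guess rate, f the fraction of untied draws in which the guess is acted on, and s the share of patients open to steering. If all steering runs the same way (likely adherers towards the app), the risk difference is

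2(c - 0.5) × f × s × (0.60 - 0.20).

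Section 4.3 gives wide discretion only for ages 13-21, so s = 0.5. With c = 0.68:

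- f = 0.25: 0.36 × 0.25 × 0.5 × 0.40 = 0.018; risks 0.391 and 0.409; RR 0.96.
- f = 0.50: 0.36 × 0.50 × 0.5 × 0.40 = 0.036; risks 0.382 and 0.418; RR 0.91.

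With c = 0.52 or 0.53 the difference is at most 0.06 × 0.50 × 0.5 × 0.40 = 0.006, and the RR is about 0.99. Direct simulation agrees. With f = 0 the RR is 1.

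**Step 4: is one central list enough?** With 50 younger and 50 older patients on one balanced, unstratified list, the chance of exactly 25 younger patients per arm is C(50,25)²/C(100,50) = 0.158, about 16%. The age target therefore needs one list per age group.

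**The case against.** The strongest reply is that the main premise is not in the documents. Section 5.2.1 speaks of a single list, and a reader who infers that each hospital works through its own run is going beyond the text. If the envelopes are drawn across sites, the guess rate is about 52% and the effect is negligible. This stands, and the 67-68% is conditional on it. The plan does not secure the safer case, however, and with physical envelopes and three hospitals local runs are plausible.

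Second, section 5.2.2 says enrolling staff are unmasked. It does not say that one recruiter sees or tallies every allocation at a site. With several recruiters, each knowing only their own patients, the rate would be lower. This also stands, so 67-68% is an upper figure.

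Third, a reader might apply steering to every untied draw in both age groups, which gives RRs of about 0.91 and 0.83. Section 4.3 does not support that, because the window for older patients is narrow. Opposite motives (reliable patients to the app, or struggling patients to the app) would also partly cancel.

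Fourth, numbered sealed envelopes with varying blocks are a recognised method, and a reader might wrongly infer that paper leaves no audit trail. REDCap logs every screening and enrollment, and section 10.3.1 requires signed and dated source records. That helps an audit afterwards, but it does not stop guessing beforehand.

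**Conclusion.** The concern holds in conditional form. The plan combines unmasked enrolling staff, envelopes in small blocks and no stated custody. Under local, fully visible runs the next arm can be guessed about 67-68% of the time, against about 52% under one central list with own-site view and 50% by chance. This is an advantage on average, not knowledge of the next arm.

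The illustrative distortion is an RR of about 0.96 or 0.91 with no app effect. It rests on the assumed risks of 20% and 60%, an even mix of the two patient types, steering confined to ages 13-21 and all in one direction, and the guess acted on in 25% or 50% of untied draws. None of these assumptions comes from the documents except the wider discretion for the younger group. A reader might infer that recruiters will steer or that the trial will be biased. The documents show an opportunity only, and without steering there is no bias. The case for change is that the safer method costs little and the trial already has the system for it.

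**What to change.** In the synopsis and sections 4.3 and 5.2.1, replace the envelopes with allocation from pre-generated random-block lists held in the central REDCap system and hidden from all enrolling staff.

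- Use one central list per age group (13-21; 22 and older), drawn in enrolment order across the three hospitals. Choose the last blocks so that each list closes at 25 per arm. Do not split the lists by site, because short site runs would restore the predictability.
- Release each assignment, time-stamped, only after REDCap records consent, eligibility and the completed baseline survey.
- Adjust for age group in the primary analysis in section 9.
- Moving the block-size range out of the protocol is optional, since the tally guess does not need it.

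The cost is a short amendment and REDCap set-up, with no extra patients or visits. The downside is that system access is needed at the moment of allocation. For phone or off-line enrolment, the coordinating center can release the assignment.

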5.2.2 Blinding

Research team members responsible for enrollment and reviewing emocha app submissions will not be masked to who is in the intervention or control arm. Patients will be aware of which arm they are randomized to as well. In this sense, the study will not be blinded to patients. Furthermore, patients/families will be strongly discouraged from discussing with their clinical team to which treatment arm they are enrolled. Data extraction (labs, drug levels) will be performed by study personnel that are blinded to the treatment arm. Individuals performing data analysis will receive de-identified data that does not explicitly describe which group is intervention and which is control, but simply the code without a key. Only the PI at each site and necessary personnel performing data extraction will have the key for the code to minimize bias in data analysis.

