1.2 Secondary Objectives

- Clinical endpoints including rejection and hospitalization
- Patient reported adherence on immunosuppressant therapy instrument (ITAS)
- Patient-reported QoL outcomes as measured by PedsQL and SF-36
- Patient-reported self-efficacy using the Riekert Self-efficacy scale
- Patient-reported usability using the PSSUQ (treatment arm only)
- To examine the patterns of medication adherence in transplant recipients in both groups to better understand baseline medication adherence
- To understand the feasibility and acceptability of implementing such a system into the clinical workflow and patient follow-up care management

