9. STATISTICAL CONSIDERATIONS

Primary outcome variables:

12-week immunosuppression medication adherence:

We will measure medication adherence in both arms at 12 weeks. The Medication Level Variability Index (MLVI) will be used to analyze immunosuppression lab

values to determine adherence with a relative risk noted for standard deviation >2 .

Secondary outcome variables:

- Hospitalization days
- Biopsy-proven rejection
- Clinician-assigned rejection

We will recruit 100 liver and kidney transplant recipients (50/arm), and compare recipients who received the mHealth intervention to controls that did not receive it. The Medication Level Variability Index (MLVI) will be used to analyze immunosuppression lab values to determine adherence with a relative risk noted for standard deviation >2 . Descriptive statistics will be performed to compare frequencies of secondary outcomes (e.g., hospitalization, rejection, etc). Patient reported outcomes will be scored as appropriate and differences compared between treatment arms. Additionally, we will perform subgroup analyses for younger transplant recipients (age at transplant <40), older transplant recipients, men, and women.

In addition to understanding the efficacy of this technology in a transplant patient population, we will also evaluate the feasibility of implementing such a system into clinical workflow. We will examine time spent by reviewers each week using mDOT, most ideal time post-transplant to consent and educate participants on using the application, and streamlining the workflow involved in the application. In order to ensure acceptability among the patients who will be using the app, we will survey all participants in the intervention arm at the end of the study period on their overall satisfaction in using the app. This survey will be administered with the ITAS scale over the phone. In addition, we will also examine consent rate and use of the mDOT app by participants over time to understand acceptability of using the application.

Feasibility will also be measured through phone interviews with all study participants at 12 months. We will contact all patients who consented to be in the study to participate in the phone interviews. The interviews will be semi-structured, with a set of pre-written questions as the guide. All interviews will be audio recorded. Transcription of the interviews will be conducted by Production Transcripts, Inc.

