10.3 Data Management and Monitoring

10.3.1 Source Documents

Source documents for this study will include the subjects' medical records and study record documents. If the investigators maintain separate research records, both the medical record and the research records will be considered the source documents for the purposes of auditing the study. The local site investigator will retain a copy of source documents. The local site investigator will permit monitoring and auditing of these data, and will allow the sponsor, IRB and regulatory authorities access to the original source documents. The local site investigator is responsible for ensuring that the data collected are complete, accurate, and recorded in a timely manner. Source documentation (the point of initial recording of information) should support the data collected and entered into the study database/case report form and must be signed and dated by the person recording and/or reviewing the data. All data submitted should be reviewed by the site investigator and signed as required with written or electronic signature, as appropriate. Data entered into the study database will be collected directly from subjects during study visits or will be abstracted from subjects' medical records.

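### Masked extraction is promised only for labs and drug levels, not for rejection or hospitalization, and section 5.2.2 also gives the code key to the extractors it calls blinded

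*Combined protocol and SAP*

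**What the plan says.** The study is open to participants and partly open to staff. On staff, section 5.2.2 says "Research team members responsible for enrollment and reviewing emocha app submissions will not be masked to who is in the intervention or control arm". On extraction it says "Data extraction (labs, drug levels) will be performed by study personnel that are blinded to the treatment arm". Analysts receive coded data without the key, and the section then states who does hold it: "Only the PI at each site and necessary personnel performing data extraction will have the key for the code". The treating team is protected only indirectly, in that "patients/families will be strongly discouraged from discussing with their clinical team to which treatment arm they are enrolled".

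Section 1.2 lists among the secondary objectives "Clinical endpoints including rejection and hospitalization". Section 9 turns these into three outcome variables: days in hospital, rejection proven by biopsy, and "Clinician-assigned rejection". They are to be compared descriptively. The last has no definition, and no adjudication is planned.

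The schedule in section 5.1 has one row for immunosuppression levels and laboratory values and a separate row for interval health information at 3, 6, 9 and 12 months. It names no collector for the second row and gives no masking status. Section 10.3.1 says that data come from participants or from their records, and adds: "All data submitted should be reviewed by the site investigator and signed as required with written or electronic signature, as appropriate".

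**The concern.** Masking of extraction does most good where the person reading the chart has to decide something. A tacrolimus level is a number to copy. Whether a set of notes amounts to a clinician's diagnosis of rejection can be a matter of reading. The plan states its protection for the first kind of data and is silent on the second.

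If someone who has reviewed a participant's dosing videos also abstracts that participant's rejection episodes, an expectation about the app can affect which borderline episodes are recorded. Coded data at the analysis stage cannot undo differential recording upstream. These three variables are the only clinical outcomes listed in section 9, so it matters that they can be trusted.

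The key adds a second difficulty. If extractors can look up the arm, the masking that is promised for labs and drug levels is not secure either, and those data determine the primary outcome.

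**Working it through.** The plan gives no figure to reproduce, so the check is mainly a comparison of sections.

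**Step 1. Which outcomes does the masking promise cover?**

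| Data | Role | Masked extraction stated (5.2.2)? | Room for judgement at abstraction |
|---|---|---|---|
| Drug levels (MLVI) | Primary | Yes | Little |
| Hospitalization days | Secondary | No | Little |
| Biopsy-proven rejection | Secondary | No | Little |
| Clinician-assigned rejection | Secondary | No | Most |

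The last column is my assessment; the other columns come from sections 5.2.2 and 9. Sections 5.1, 5.2.1, 5.2.3, 9 and 10.3.1 do not extend the promise.

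**Step 2. Who may collect the uncovered outcomes?** Section 5.1 names nobody, and section 10.3.1 describes the source of the data but not the collector. Section 5.2.2 identifies two unmasked groups, enrolment staff and video reviewers. No section bars either from abstracting clinical events. Unmasked abstraction is therefore allowed, though not prescribed.

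**Step 3. Are the extractors masked?** One sentence of section 5.2.2 says that those extracting labs and drug levels are blinded to arm. A later sentence lists necessary extraction personnel among the key holders. The code in question is the one that conceals which group is which from the analysts, so its key reveals the arm. The two statements cannot both hold for the same people.

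**Step 4. Who reviews the entries?** Section 5.2.2 gives the key to the PI at each site. Section 10.3.1 has the site investigator review submitted data. If these are the same role, which is the natural reading but is not stated, the reviewer of outcome entries can know the arm.

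**Step 5. Illustration of size.** Section 9 gives 50 participants per arm. The event rate is an assumption. With a true rate of 20% in both arms, expected events are 50 × 0.20 = 10 per arm. If k app-arm events go unrecorded and no control events do, the observed relative risk is RR = [(10 − k)/50] / (10/50) = (10 − k)/10.

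- k = 1: 9/10 = 0.90
- k = 2: 8/10 = 0.80
- k = 3: 7/10 = 0.70

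The effect of one lost chart depends on the assumed rate. At 10% (5 events) it gives 4/5 = 0.80; at 30% (15 events) it gives 14/15 = 0.93.

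The losses above are 10–30% of all app-arm events. If only half of the 10 events were ambiguous and 10–30% of those were lost, 0.5 to 1.5 events would go and RR would be 9.5/10 = 0.95 to 8.5/10 = 0.85.

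For 7/50 against 10/50, the standard error of log RR is √(1/7 − 1/50 + 1/10 − 1/50) = 0.450. The 95% interval is exp(ln 0.70 ± 1.96 × 0.450), or about 0.29 to 1.69. Even the largest distortion considered lies well within chance variation for a trial of this size.

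**The case against.** **The parenthesis may only give examples.** Clinical events sit in the same medical records, and the later mention of data extraction in section 5.2.2 carries no such limit. This reading is possible. But the wording does not mark the two items as examples, and the schedule separates laboratory data from interval health information. At best the text is ambiguous, and the same amendment resolves it.

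**The key sentence may be a slip.** Extractors need the link between study number and patient to find the chart, and sections 6.1 and 10.1 describe a separate database holding that link. The authors may have meant that link and not the arm key. That would be a sensible arrangement, but it is not what the sentence says.

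**The bias starts elsewhere.** Clinician-assigned rejection is decided by the treating clinician, and an abstractor only records it. This objection stands. Patients are merely discouraged from disclosing their arm, so a masked abstractor may faithfully copy an unmasked judgement. Masked abstraction removes one source of bias and leaves this one.

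**The investigator's review is a quality duty.** A reader might infer that the key-holding PI has the last word on every outcome and could remove events. The documents do not support that. Section 10.3.1 says data should be reviewed and signed as required, makes the investigator responsible for completeness and accuracy, requires source documents to support entries, and opens those documents to audit.

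**The consequence is limited.** These are secondary outcomes compared descriptively, and two of the three are largely objective. This also stands, and it limits the weight of the point.

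**Conclusion.** The point holds in two parts. First, masked extraction is promised for labs and drug levels only, so the plan as written allows unmasked staff to abstract hospitalization and rejection. Clinician-assigned rejection is materially exposed; biopsy-proven rejection and hospital days are much less so. Second, section 5.2.2 contradicts itself on whether extractors can see the arm, so masking is not assured even for the data behind the primary outcome.

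A reader might go further in three ways. One is to conclude that unmasked staff will abstract these outcomes; the documents only fail to prevent it. Another is to conclude that MLVI is biased. The contradiction makes its masking insecure, but copied laboratory values leave little room for expectation to act. The third is to read 0.90 to 0.70 as an estimate of bias. It is an illustration that rests on an assumed 20% rejection rate and an assumed one-sided loss of 1 to 3 events. What it does show is that, with about 10 events per arm, a few charts can produce an apparent benefit.

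The change is worth making because it is cheap and specific. The concern about outcome abstraction is confined to secondary, descriptive comparisons.

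**What to change.** In section 5.2.2:

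- Extend masked extraction to hospital admissions, biopsy results and clinician-assigned rejection. It should be done by the existing masked extractors and not by enrolment or video-review staff.
- Remove the arm key from both the extractors and the site PI. Hold it at the coordinating center, with staff who neither extract nor sign off outcomes, until database lock. Analysts continue without it. Extractors keep only the study-number-to-patient link that they need to find the chart.

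In section 10.3.1: have outcome forms reviewed and signed without the arm field.

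In section 9: state as a limitation that masked abstraction does not remove bias in the treating clinician's own judgement, because patients are only discouraged from disclosing their arm. A written definition of clinician-assigned rejection with masked adjudication would address part of this, if the sponsor is willing to go further.

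The cost is protocol wording and some reassignment of tasks at sites, where the same few people may now cover several roles. No visit, procedure or new data item is needed. Adjudication, if adopted, would be additional work.
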